10.3 Study specific exemptions

For women who become pregnant during the trial exemptions include any event during the birth/birth process that relates to the process of delivery (e.g. hospitalisation for normal vaginal delivery, planned C-section, episiotomy etc.) will not be recorded as an AE or SAE (information regarding miscarriage and emergency C-sections will be collected on the CRF).

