13. Adverse events due to procedure related and gynaecological/obstetric related complications (see section 10)

Health Economics

14. Health resource use of the participant measured at baseline, 6, 15 and 24 months post randomisation.
15. Patient costs measured following hysteroscopy for participants randomised to hysteroscopic resection
16. Cost per live birth gained.

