10.2 Recording and reporting

AEs and SAEs are defined as an event that occurs after the patient has provided written informed consent for trial entry and up to completion of the 24 month follow-up by the last participant recruited (LPLV).

Hysteroscopic resection of submucous fibroids and endometrial polyps is a routine procedure for which the side effects are understood. Therefore, only those AEs which are deemed serious or of particular relevance to the procedure will be recorded / reported in this trial. These are listed as 'expected AEs' in Table 4.

Adverse Events

Participants will be asked for any details of adverse events, at four time points up to the participants' final study related follow-up event; post procedure (if randomised to receive hysteroscopic resection of submucous fibroids or endometrial polyps), then at 6, 15 and 24 months post randomisation. AEs or SAEs may also be identified by the Research Nurse/Associate PI/Dr, or any other individual, at any point during the study, up to last patient last visit.

When an event is identified the process for recording and reporting outlined in Figure 5 will be followed. The local PI (or other suitably trained member of research staff, if the task is delegated to them) should be notified immediately and assess the event for classification as an SAE (see definition in section 10.1).

AEs confirmed as NOT serious will be checked against the list of expected AEs (Table 4).

Expected AEs

AEs which are expected will be recorded by site staff in the participant CRF.

Unexpected AEs

AEs which are not expected will not be recorded on the basis that hysteroscopic resection of submucous fibroids and endometrial polyps is a routine procedure, for which the side effects are understood. We do not anticipate any AEs, which are of relevance to the intervention, other than those listed in Table 4, unless the site PI considers the events to be significant.

Sites are asked to enter all available information onto the study database as soon as possible after the site becomes aware of the event.

Table 4 - Expected Adverse Events

Gynaecological / obstetric related	Procedure related (immediate)	Procedure related (delayed)

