
● Placenta accreta, increta, percreta● Placenta abruption● Growth retardation● Foetal distress● Antepartum haemorrhage● Post-partum haemorrhage● Placenta Praevia (grade 3 & 4)● Placental abruption● Manual removal of placenta	
● Uterine perforation● Bowel injury● Bladder injury● Significant bleeding during the procedure resulting in additional intervention● Air embolism (though this is very rare and more commonly associated with resection of Type 2 submucous fibroids)● Fluid overload and hyponatremia● Vasovagal reaction (hypotension and fainting) requiring additional intervention during the procedure (e.g. presence of anaesthetist) OR after the procedure● Return to theatre immediately	
● Post-operative adhesions requiring intervention● Infection

Serious Adverse Events

All AEs classed by the PI or delegate as serious will require more detailed information to be recorded in the participant CRF. In such cases, the event must also be reported to the Sheffield CTRU within 24 hours of the site becoming aware of the event (see section 10.4).

[figure not shown]
Expected Serious Adverse Events

Expected SAEs are those events listed in Table 4 which are assessed as serious using the definition in section 10.1.

Unexpected Serious Adverse Events

All unexpected serious adverse events should be assessed for causality by the PI or delegate. Following reporting of these events within 24 hours by site staff to the CTRU, all unexpected SAEs will be reported by the CTRU to the sponsor and DMEC. SAEs which are unexpected and related / suspected to be related to the intervention will be reported further by the CTRU to the REC within 15 working days.

Figure 5 - Recording and reporting of AEs and SAEs

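### The delivery exemption in section 10.3 is too broad and conflicts with Table 4, so it is unclear whether complications at birth count as adverse events

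*Protocol*

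**What the plan says.** Four parts of the protocol bear on this.

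- **Outcome 13 (section 8.3)** is "Adverse events due to procedure related and gynaecological/obstetric related complications", and it refers the reader to section 10 for its content.
- **Section 10.2** restricts recording to serious events and to those of particular relevance, listed in Table 4. For the latter it says "AEs which are expected will be recorded by site staff in the participant CRF". A Table 4 event that meets the seriousness definition in 10.1 becomes an expected SAE, and all SAEs go to the trials unit within 24 hours.
- **Table 4**, obstetric column, includes "Post-partum haemorrhage", "Manual removal of placenta" and "Foetal distress", together with the placenta accreta group and abruption.
- **Section 10.3** exempts, for women who become pregnant, "any event during the birth/birth process that relates to the process of delivery". Its examples are "hospitalisation for normal vaginal delivery, planned C-section, episiotomy etc". The exempted events "will not be recorded as an AE or SAE (information regarding miscarriage and emergency C-sections will be collected on the CRF".

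Section 11.2 compares adverse events between the randomised groups, with a test and a 95% confidence interval. Section 10.6 gives the DMEC and TSC information on AEs and SAEs.

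**The concern.** Some Table 4 events are by nature events of delivery. Manual removal of the placenta hardly arises anywhere else. A site that takes 10.3 at its word would not record such an event. A site that follows 10.2 would record it and, if it were serious, report it within 24 hours.

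The protocol evidently wants these events. Section 10.2 selects them as relevant to the procedure, and the amendment log shows the placental items being extended in version 2.0. At stake are the completeness of part of outcome 13 and the route by which a serious maternal event reaches oversight. Section 10.6 covers AEs and SAEs, so an event that carries neither label has no stated path to the DMEC.

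**Working it through.** This is a comparison of texts. The plan gives no figure to reproduce.

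**Step 1. Which Table 4 events fall within the words of 10.3?** The obstetric column has nine lines and eight distinct items, because abruption is listed twice.

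| Table 4 item | Does 10.3, read literally, exempt it? |
|---|---|
| Post-partum haemorrhage | Yes: at or directly after birth |
| Manual removal of placenta | Yes: part of delivery |
| Foetal distress | Yes, when it arises in labour |
| Placenta accreta, increta, percreta | Only when first found at delivery |
| Placental abruption | Only when it presents at delivery |
| Growth retardation, antepartum haemorrhage, placenta praevia | Largely no: mainly antenatal |

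The conflict therefore covers part of the column.

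**Step 2. What is each instruction for an overlapping event?** Take a post-partum haemorrhage that prolongs admission.

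- Under 10.1 it is serious.
- Under 10.2 it is an expected SAE, reported within 24 hours.
- Under 10.3, read literally, it is neither an AE nor an SAE.

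Both instructions cannot be followed.

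**Step 3. Does the text say which prevails?** No visible sentence does. Section 10.3 does not mention Table 4 or the seriousness definition, and 10.2 does not mention the exemption. Figure 5, which section 10.2 says governs the process, could not be seen, so a precedence rule there cannot be excluded.

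**Step 4. Do the examples in 10.3 settle it?** They point to routine delivery, but the rule says any event and the list is open-ended. The same sentence then provides for emergency C-section data on the CRF. If only routine delivery were exempt, there would be little need to say so. A careful site could conclude that non-routine delivery events are exempt unless named.

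**Step 5. Are the events captured elsewhere?** In part. Table 2 schedules obstetric complications as adverse events at 6, 15 and 24 months, and has a separate row for obstetric outcomes whose content is not defined. Section 10.4 requires congenital anomalies and neonatal deaths to be entered in the database. None of these says whether a maternal delivery event listed in Table 4 is an AE or SAE despite 10.3.

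**Step 6. Scale, for illustration only.** Section 11.1 plans 560 women per trial, so 560 / 2 = 280 per arm, with live birth rates of 10% (control) and 20% (intervention) by 15 months.

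- Control: 280 × 0.10 = 28 women with a live birth.
- Intervention: 280 × 0.20 = 56.
- Together: 28 + 56 = 84 per trial.

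The protocol gives no rate for these complications. Assuming 5% to 20% of births:

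| Assumed rate | Control | Intervention | Total per trial |
|---|---|---|---|
| 5% | 1.4 | 2.8 | 4.2 |
| 10% | 2.8 | 5.6 | 8.4 |
| 20% | 5.6 | 11.2 | 16.8 |

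These are events whose recording could depend on the section followed. They are not expected losses, because the share of sites that would read 10.3 broadly is unknown. Recording continues to the last patient's last visit, so births after 15 months would add to them.

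**The case against.** The strongest defence is that 10.3 should be read with its examples. All are routine, and 10.1 counts any inpatient admission as serious, so without an exemption ordinary births would generate SAE reports. Table 4 names post-partum haemorrhage and manual removal of the placenta specifically, and reading 10.3 to override those entries would leave them almost without content. This stands as an account of intent. A reader might infer from 10.3 that the protocol decided to discard delivery complications, and the documents do not support that. But intent does not remove the literal conflict that site staff face.

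A reader might also infer that the between-arm comparison is biased, since more births, and so more affected events, are planned in the resection arm. The protocol does not show this. Randomisation is stratified by centre, so a site that applies one reading consistently applies it to both arms. The two-to-one split above only restates the assumed live birth rates. Site staff are unblinded, so case-by-case discretion could in principle differ by arm, but nothing in the protocol indicates that it would.

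On oversight, section 10.2 singles out unexpected SAEs for forwarding to the sponsor and DMEC, whereas serious Table 4 events are expected SAEs. Under 10.4 and 10.6 they would still come to the DMEC at regular intervals. What is at risk is chiefly that periodic review and the 24-hour report to the trials unit, and only where a site takes the broad reading.

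The double entry for abruption is clerical. That one event would be counted twice is speculation.

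**Conclusion.** The wording of 10.3 conflicts with 10.2 and Table 4 for a defined set of events: post-partum haemorrhage, manual removal of the placenta, foetal distress in labour, and accreta or abruption first found at delivery. The conclusion rests on the literal text and on there being no precedence rule in what can be read, with Figure 5 unseen.

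The probable consequence is under-recording, or recording that differs between sites, in part of one secondary safety outcome, and some serious Table 4 events not reported as SAEs. Its size cannot be derived from the protocol. The 4 to 17 events per trial by 15 months rest on an assumed complication rate and count every such event as at risk. The primary outcome, the sample size and the immediate procedure-related harms are unaffected. This should be fixed, and it is not a defect that undermines the trial.

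**What to change.** Reconcile 10.2, Table 4 and 10.3 in two steps:

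1. Limit the 10.3 exemption to routine delivery events such as those it already lists.
2. Add one sentence: events listed in Table 4 are recorded, and are reported as SAEs if they meet section 10.1, even when they occur during birth.

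Check that Figure 5 says the same. The repeated abruption line can be removed at the same time.

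The sentence should not extend to every delivery event that meets 10.1. That definition counts any prolonged admission as serious, so the wider wording would largely undo the exemption and bring many more events into 24-hour reporting.

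The cost is a short amendment, a note to sites and a few more AE or SAE forms. No visit or procedure is added.

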10.4 SAE recording and notification procedure

All SAEs should be reported to the CTRU within 1 working day from the point of identification.

Sites should try and enter a diagnosis into the reporting form. If a diagnosis is unknown at the time of submission to CTRU, the form may be updated at a later date.

SAE notification procedure

- Sites should notify Sheffield CTRU of all unexpected SAEs immediately but within a maximum of 1 working day from the point of identification. Congenital anomalies and neonatal deaths will be reported using the study database as soon as possible after the event is identified.
- Details will be recorded on a SAE form (filed in the Investigator site file or downloaded from the AE eCRF page) and can be sent to the Sheffield CTRU via the following methods:
 - **Email:** Completed SAE report forms should be emailed to the dedicated email address ([contact]). The email account will be checked during office hours (between 9am and 5pm Monday to Friday).
- In the event that no clinical assessment can be made immediately, it is recommended that the SAE form is sent to the CTRU regardless, and an assessment is obtained as soon as feasible on a new SAE form and forwarded to the CTRU in Sheffield.
- Follow-up or corrections to information should also be reported on a new SAE form and forwarded to the CTRU in Sheffield.
- Sheffield CTRU will be responsible for reporting SAEs to the sponsor, the DMEC and the REC.

All SAEs will be reviewed by the DMEC at regular intervals. The CI will inform PI's concerned of relevant information that would adversely affect the safety of the participants.

10.5 CTRU responsibilities

The Sponsor usually delegates CTRU responsibility for the reporting of SAEs to the regulatory authorities and the research ethics committee, as appropriate. CTRU will also keep all investigators informed of any safety issues that arise during the course of the study.

10.6 SAE additional reporting

The DMEC and TSC will also receive information on all AEs and SAEs, at a frequency agreed with each committee and documented in the appropriate charter/terms of reference.

11. Statistics

11.1 Sample size

The primary outcome for both trials will be live birth rate (LBR) defined by the number of live births after 24 weeks gestation within the 15-month post-randomisation follow-up period relative to the number of women randomised.

Our review of the research literature including a Cochrane review of hysteroscopic removal of submucous fibroids and endometrial polyps (6) has found no reported estimates of the LBR in our proposed target populations. Although, two previously conducted RCTs included in the Cochrane review roughly indicate a doubling of pregnancy rates. The first quoted a clinical pregnancy rate (at 6-7 weeks) of approximately 214/1000 (21%) over 12 months in a sample of 42 women with fibroids (submucosal and mixed submucosal intramural) without surgery and a miscarriage rate (between 7 and 12 weeks) in those without surgery of approximately 556/1000 (56%) (35). Applying the miscarriage rate to the pregnancy rate (i.e. $0.21 * 0.56$) would give a LBR of approximately 10% over 12 months in the control arm (no resection). The second, in women with endometrial polyps undergoing IVF, detected an increase of pregnancy rates from 28% to 63%, with no miscarriage rate reported (36). We therefore estimate a usual care LBR of 10% within 15 months in the populations of women proposed for inclusion in this study, both for the submucous fibroid and endometrial polyp RCTs.

Assuming a 10% LBR in the no hysteroscopic removal (control) group and that an absolute increase of 10%, to a 20% LBR (a relative risk of 2.00) in the hysteroscopic removal (intervention) group is of clinical and practical importance. Then to have a 90% power of detecting this difference or more, in LBR rates between the groups, as statistically significant at the 5% two-sided level, will require 266 women per group (532 in total). Adjusting for a predicted attrition rate of 5% (due to potential difficulties of follow-up for patients who have been referred from other NHS Trusts) we will require 560 participants to be randomised.

A similar sample size will be required for RCT2 (polyp population) i.e. 560 participants, so a total of 1120 participants are required for RCT1 and RCT2 combined.

We will verify the 10% control group LBR used to inform the sample size calculation by conducting two interim assessments. The first interim analysis will be undertaken using the clinical pregnancy outcome once 50% of the target number of participants have been randomised. The clinical pregnancy outcome can be regarded as a proxy or surrogate outcome for the primary outcome the live birth rate, and allows for an earlier interim assessment to be made.. If the clinical

pregnancy rate outcome is greater than or equal to 10% we will continue to the 2nd interim assessment, using the primary outcome variable.. If the clinical pregnancy rate outcome is less than 10%, then the DMEC will then make a recommendation to the TSC regarding any need to alter the sample size of one or both of the trials.

Note: Clinical pregnancy rate is defined by an observation of viable intrauterine pregnancy with a positive heart pulsation seen on ultrasound at/after 8 weeks gestation

The 2nd interim assessment will be undertaken once 50% of randomised participants have been followed up for 15 months. With live birth data on approximately 50% (280/560 women per trial) we will be able to estimate the LBR within +/-5% (i.e. 95% CI: 5% to 15%). As we anticipate the endometrial polyp trial will recruit quicker than the submucous fibroid trial, and the control group LBR rate may differ between these two populations, this assessment will be undertaken in the two trials separately, at different time points. Both interim assessments will be undertaken by the DMEC, who will then make a recommendation to the TSC regarding any need to alter the sample size of one or both of the trials.

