
Duration of recruitment period and first enrolment date
	
Duration of recruitment period: 2 years and 6 months (pre-COVID-19 pandemic plan)

	First enrolment date for the pilot phase will be July 2021
Duration of follow-up	Minimum of 24 months post-randomisation (participants to be followed up to the last participant completing the 24-month data collection) Long-term follow up at least 5 years post randomisation
Target sample size	1120
Definition of end of trial	Completion of the 24-month follow-up by the last participant recruited (last patient last visit, LPLV)

2. Introduction

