Patients and clinicians will not be blinded to which arm of the study the participant is randomised to, due to the nature of the intervention. The primary outcome of live birth rate will be collected at 15 months post randomisation, with participants being followed-up at 6 months, 15 and a minimum of 24 months post-randomisation. The pre-COVID-19 plan for recruitment was 2.5 years. Women recruited to the trial will have at least 4.5 years follow-up in the main trial (randomisation to 24mth follow-up plus 2.5 years to last patient last visit, LPLV). Participants will be followed up for an additional 3 years in the long term study.

An economic evaluation will be undertaken to determine the cost-effectiveness of submucous fibroid and endometrial polyp resection.

Internal pilot

Each trial will commence with a 9-month internal pilot phase across approximately 30 sites to determine whether the recruitment strategy and site set-up are feasible, whether participants randomised to intervention receive resection within an acceptable timeframe (set at 3-months post randomisation) and whether the level of withdrawal from the control treatment (i.e.the numbers of women in the control arm who undergo resection) is acceptable. The pilot study will use the same trial procedures as later described for the main trial.

[figure not shown]
Main study

Following successful completion of the internal pilot, each trial (RCT1 and RCT2) will aim to recruit a total of 560 patients from approximately 30 centres across the UK, over 30 months (recruitment target includes participants recruited to the 9-month internal pilot). Eligible women will be randomised to receive either hysteroscopic resection of the abnormalities (intervention group) or no hysteroscopic resection (control group).

Long term follow-up study

A long term follow up study will be undertaken using data available in medical notes and / or routine NHS data – each participant will be followed up for a minimum of 5 years to collect pregnancy outcomes, fertility treatment and whether hysteroscopic resection of the abnormalities has been undertaken. Participants will be asked at recruitment if they are willing for the research team to access this data from hospital/clinic medical records and from NHS Digital; participants will indicate permission for this on the trial consent form.

Figure 2 Trial summary flow

5. Selection of participants

Trial Setting

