8.1 Feasibility outcomes

We have followed the recommendations of Avery et al in setting green/amber/red criteria for both RCTs (34), where green indicates continuation of the trial, any amber indicates that steps should be in place to regain ground and any red indicates the trial is not feasible. Targets will be assessed following 9 months of a 30 month recruitment window. Recruitment targets factor in a staggered site set-up over 7 months. Participant retention will not be assessed as the primary outcome data collection point occurs at 15 months post-randomisation and so inclusion within the stop/go assessment timeframe is not possible.

It is anticipated that the COVID-19 pandemic will impact site waiting times for hysteroscopic resection and these will be monitored during the pilot phase. Timing of primary outcome measurement may require adjustment following this assessment.

If assessment against the criteria indicates that one of the two trials is feasible and the other infeasible, recruitment to the infeasible trial will stop. Only the trial for which recruitment has been feasible will continue. As we anticipate a higher incidence rate in the endometrial polyp trial, a lower than target recruitment rate would therefore still allow completion within the allocated project timescales.

At the end of the pilot phase, the Trial Steering Committee (TSC) will make a recommendation to the NIHR (funder) on whether the feasibility criteria have been met and whether the trial should continue. The TSC may report to the NIHR earlier if the trial meets the feasibility criteria below earlier than expected. Sheffield CTRU will aggregate feasibility of the research and intervention protocols based on the following criteria.

Table 1 Progression criteria for pilot to main trial

Domain	Target at 9m	Green	Amber	Red
Site set-up	30 centres setup and recruited and randomised at least one participant	25 or more centres recruited and randomised at least one participant	15-24 centres recruited and randomised at least one participant	Fewer than 15 centres recruited and randomised at least one participant

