Participant recruitment	
Fibroids RCT Average of 0.67 participants recruited per centre per month (approx. 117 in total)
 
Polyps RCT Average of 1.3 participants recruited per centre per month (approx. 227 in total)
	
Fibroids RCT Minimum 80% of target (per centre per month)
 
Polyps RCT Minimum 40% of target (per centre per month)
	
Fibroids RCT 60-80% of target (per centre per month)
 
Polyps RCT 30-40% of target (per centre per month)
	
Fibroids RCT Below 60% of target (per centre per month)
 
Polyps RCT Below 30% of target (per centre per month)

Number of women randomised to intervention (resection) and receiving resection treatment within three months of randomisation*	100% of intervention participants received intervention before 3 months post randomisation	80% of intervention participants received intervention before 3 months post randomisation. No change to timing of primary endpoint e.g. LBR at 15 months post randomisation.	Less than 80% of intervention participants received intervention before 3 months post randomisation. Consider a change to the primary endpoint point e.g. to 18 or 21 or 24 months post-randomisation	Not applicable.

Withdrawal from control treatment (receiving resection) before 6 months post randomisation	0% of control participants received intervention before 6 months post randomisation	Fewer than 10% of control participants received intervention before 6 months post randomisation	Between 10-50% of control participants received intervention before 6 months post randomisation	Greater than 50% of control participants received intervention before 6 months post randomisation
--------------------------------------------------------------------------------------------	-------------------------------------------------------------------------------------	-------------------------------------------------------------------------------------------------	-------------------------------------------------------------------------------------------------	---------------------------------------------------------------------------------------------------

Note: Fulfilment of the 'green' criteria indicates continuation of the trial, fulfilment of the amber criteria indicates that steps should be in place to regain ground, fulfilment of the red criteria indicates the trial is not feasible.

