11.2 Statistical Analysis

Data from the two trials will be analysed and reported separately. Both trials have the same primary and secondary outcomes so the analysis and reporting will be similar. As both trials are pragmatic parallel group RCTs, data will be reported and presented according to the latest CONSORT guidelines. The statistical analyses will be performed on an intention-to-treat basis. Under the strict intention to treat (ITT) principle, all women will be included in the analysis once they are randomised as per the allocated treatment regardless of what happens after randomisation. All statistical exploratory tests will be two-tailed with alpha = 0.05.

Interim Analysis

There is no formal planned interim analysis other than the assessment of recruitment, treatment uptake and withdrawal from randomised treatment allocation after the 9-month internal pilot phase, and the assessments of clinical pregnancy and live birth rates in the control arm after 50% of randomised participants have been randomised and followed up for 15 months, respectively.

At the first interim assessment, the clinical pregnancy rate will be calculated in the control arm. If lower than the 10% estimate used for LBR in the control arm in the sample size estimation, sample size re-estimation will be considered, under the guidance of the DMEC. If greater than or equal to 10%, no adaptation will be made and the next interim assessment will take place when 50% of participants have completed the 15-month follow-up.

At the second interim assessment we shall calculate the LBR and its associated 95% CI for participants in the control arm. If the CI includes the 10% LBR (which we assumed for the control group in the sample size calculation) then we will continue to recruit to the original target sample size.

If the CI for the LBR in the control arm does not include 10% then we will re-estimate the sample size using the point estimate for the LBR we have observed thus far in the control arm and the same target difference of 10%. If this results in a reduction in the target sample size we will continue to recruit to the original target sample size (of N=560). If this results in an increase in the target sample size we will seek the opinion of the independent DMEC and TSC about increasing the sample size.

Baseline assessments

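### If recruitment goes to plan, the live-birth interim meant to re-estimate the sample size falls after the last randomisation: by about 8 months for polyps, and by about 1 month (a near-tie) for fibroids

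*Protocol*

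**What the plan says.** Section 11.1 plans two checks of the assumed 10% control live birth rate (LBR). The first uses clinical pregnancy once half the target number has been randomised. The second uses the primary outcome: "The 2nd interim assessment will be undertaken once 50% of randomised participants have been followed up for 15 months", which the section equates with 280 of 560 women per trial.

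Section 11.2 gives the actions.
- **First look.** A control clinical pregnancy rate below 10% leads to sample size re-estimation being considered. At 10% or above nothing is changed.
- **Second look.** If the 95% CI for the control LBR covers 10%, "then we will continue to recruit to the original target sample size". If it does not, N is recalculated from the observed control rate with the same 10-point difference. A smaller N is not adopted. A larger N goes to the DMEC and TSC for an opinion.

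The recruitment plan is in section 4 (Main study): "each trial (RCT1 and RCT2) will aim to recruit a total of 560 patients from approximately 30 centres across the UK, over 30 months". Table 1 in section 8.1 gives the targets. For fibroids it says "Average of 0.67 participants recruited per centre per month (approx. 117 in total" and for polyps "Average of 1.3 participants recruited per centre per month (approx. 227 in total", both at 9 months. Section 8.1 adds: "Recruitment targets factor in a staggered site set-up over 7 months". The Trial Summary gives the recruitment period as "2 years and 6 months (pre-COVID-19 pandemic plan" and states no replacement.

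**The concern.** The second look needs women who already have 15 months of follow-up, while its actions presuppose that women are still being randomised. The protocol nowhere compares the date of this look with the end of recruitment. It has no provision to hold recruitment open, pause it or reopen it. Section 11.1 expects the polyp trial to recruit faster, which makes the timing worse there.

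The 10% assumption needs a working check. Section 11.1 says no LBR estimate was found for the target populations. The figure is built from one sample of 42 women with fibroids. For polyps, the cited trial reported 28% pregnancy without resection and no miscarriage rate. With a fixed absolute difference, a control rate above 10% raises the required N, and only the second look is written to act on that.

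**Working it through.** **Inputs.** 560 women per trial, about 30 centres and 30 months (section 4). Rates of 0.67 and 1.3 per centre per month, with 117 and 227 women by month 9 (Table 1). Trigger of 280 women with 15 months of follow-up (section 11.1). Design of 10% against 20%, 90% power, two-sided 5%, 5% attrition (section 11.1).

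**Reproducing the plan's figures.**
- The two-proportion formula with pooled variance gives 266 per group, or 532 in total; 532/0.95 = 560. This agrees.
- CI half-width with 140 controls: 1.96 × √(0.10 × 0.90/140) = 0.0497. This agrees with the stated ±5%.
- Centre-months by month 9: 117/0.67 = 174.6 and 227/1.3 = 174.6. The two targets imply the same site ramp-up.

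**Timeline at target.** Monthly rate with 30 centres: 30 × 0.67 = 20.1 (fibroid) and 30 × 1.3 = 39 (polyp). After month 9, the k-th woman enters at month 9 + (k − n9)/rate, where n9 is the 9-month total.

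| | Fibroid | Polyp |
|---|---|---|
| 280th woman | 9 + 163/20.1 = 17.1 | 9 + 53/39 = 10.4 |
| Second look (+15) | 32.1 | 25.4 |
| 560th woman | 9 + 443/20.1 = 31.0 | 9 + 333/39 = 17.5 |
| Look minus last randomisation | +1.1 months | +7.8 months |

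The gap is 15 − 280/rate: 15 − 13.9 = 1.1 and 15 − 7.2 = 7.8. The ramp-up cancels, provided the 280th woman enters after all sites are open.

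Reading the 50% as a share of women randomised so far does not help. When the 560th woman enters, about 258 fibroid women (46%) and about 24 polyp women (4%) have reached 15 months.

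**Break-even.** The look comes first only if the second 280 women take more than 15 months, that is, below 280/15 = 18.7 per month.
- Fibroid: 18.7/20.1 = 93% of target. At 0.67 per centre, 27 centres give 18.1 per month and the look falls 0.5 months before the last randomisation. With 28 centres (18.8 per month) it is still just after.
- Polyp: 18.7/39 = 48% of target.
- At break-even recruitment ends at about month 33. At the fibroid green floor (80%) it ends at month 38.0, with the look 2.4 months earlier and about 39 women left to recruit. At the polyp green floor (40%) it ends at month 39.1, with the look 2.9 months earlier and about 46 women left.
- At the rate that yields exactly 560 in 30 months with the implied ramp-up, the look is at month 31.6. With perfectly uniform accrual over 30 months the two coincide at month 30.

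**The first look.** It acts only below 10%. There the fixed 10-point difference needs fewer women: 5% against 15% needs 188 per group, and 376/0.95 gives 396.

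**What a high control rate would cost.**

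| Control LBR | Power for +10 points, 266 per group | Power, 280 per group |
|---|---|---|
| 10% | 90% | 91% |
| 15% | 82% | 84% |
| 20% | 76% | 78% |
| 25% | 71% | 73% |

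At the second look, 23 of 140 controls with a live birth (16.4%) gives a 95% CI above 10% (11.2% to 23.4%, Wilson) and a re-estimated N of about 742. With 28 of 140 (20%), N is about 826.

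**The case against.** A reader might infer that the live-birth look can never alter the sample size in either trial, so that no protection exists. The protocol does not support that, for three reasons.

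- **The fibroid result is a near-tie.** The number of centres and the 9-month totals are approximate. Table 1 rates 25 or more centres as green, and 25 centres at 0.67 (16.75 per month) put the look 1.7 months before the last randomisation. This stands. It helps only when recruitment overruns 30 months.
- **Target rates are not the only accepted rates.** For polyps, green starts at 40% of target, and section 8.1 says slower recruitment would still allow completion. Below about 48% the order reverses. The 30-month window is labelled pre-COVID, so the exact months are provisional. This also stands, but a safeguard that works only when recruitment is late does not protect a trial that recruits well.
- **An increase is not excluded.** Sections 11.1 and 11.2 leave it to the DMEC and TSC, and sites stay active for follow-up. Extending or reopening is possible, though unplanned. The accurate limit is that the rule cannot act within planned recruitment.

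Section 11.1 also says the DMEC will make a recommendation on sample size after both assessments, which could be read as letting the first look act in either direction. Section 11.2 closes that reading for rates of 10% or more.

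Finally, the harm depends on the control rate being well above 10%. Type I error and the validity of the randomised comparison are unaffected, and the base sample size reproduces.

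**Conclusion.** The concern holds in this form. On the protocol's own target rates with 30 centres, the second look follows the last randomisation by about 7.8 months for polyps and about 1 month for fibroids. The polyp result is robust down to about 48% of target. The fibroid result reverses below about 93% of target or with 27 or fewer centres, at the price of recruitment running to month 33 or later. The two-week data window, cleaning and committee review would add delay that is not counted here.

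So if recruitment goes to plan, the rule to continue or enlarge cannot act before recruitment closes, and the first look does not cover a high control rate. The cost is power of about 82% to 71% at control rates of 15% to 25%. Those rates are illustrative; the protocol gives no estimate to choose among them. Severity: should-fix.

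**What to change.** In sections 11.1 and 11.2:

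1. **Let the assessment made while recruitment is open act upwards as well.** Use clinical pregnancy as the protocol already defines it, in control women who have reached the 6-month visit. State in advance an upper threshold and a range for converting clinical pregnancy to live birth. Require the result before a named recruitment count.
2. **Settle the status of the 15-month look.** Either state that recruitment stays open until its decision is made, or call it informational and remove the statement that it can alter the sample size.

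As an illustration of timing, take the first 200 women per trial (about 100 controls). Fibroid: 9 + 83/20.1 + 6 = month 19.1, with about 321 randomised and 239 to come. Polyp: the 200th woman enters at about month 9 − 27/39 = 8.3, so the look is at about month 14.3, with about 434 randomised and 126 to come.

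The cost is protocol wording, and the pregnancy data are already collected at 6 months. The downside is a proxy with less precision: 1.96 × √(0.09/100) = ±5.9 points with 100 controls, against ±5 planned, before conversion uncertainty. It also misses later conceptions that could still deliver by month 15. The protocol supplies no reliable conversion factor, since its only pregnancy-to-birth figures come from the 42-woman sample, so a range is needed. Keeping recruitment open avoids the proxy but costs time: about 8 months for polyps at target rates.
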